16.2 Quality Assurance

Weekly registration reports will be generated to monitor patient accruals and completeness of registration data. Routine data quality reports will be generated to assess missing data and inconsistencies. Accrual rates and extent and accuracy of evaluations and follow-up will be

monitored periodically throughout the study period and potential problems will be brought to the attention of the study team for discussion and action.

Random-sample data quality and protocol compliance audits will be conducted by the study team, at a minimum of two times per year, more frequently if indicated

16.3 Data and Safety Monitoring

The Data and Safety Monitoring Plan utilized for this study must align with the MSK DSM Plan where applicable.

The Data and Safety Monitoring (DSM) Plans at Memorial Sloan Kettering were approved by the National Cancer Institute in August 2018. The plans address the new policies set forth by the NCI in the document entitled “Policy of the National Cancer Institute for Data and Safety Monitoring of Clinical Trials.”

There are several different mechanisms by which clinical studies are monitored for data safety and quality. At a departmental/PI level, there exist procedures for quality control by the research team(s). Institutional processes in place for quality assurance include protocol monitoring, compliance and data verification audits, staff education on clinical research QA, and two institutional committees that are responsible for monitoring the activities of our clinical trials programs. The committees: Data and Safety Monitoring Committee (DSMC) for Phase I and II clinical trials, and the Data and Safety Monitoring Board (DSMB) for Phase III clinical trials, report to the Deputy Physician-in-Chief of Clinical Research.

The degree of monitoring required will be determined based on level of risk and documented.

The MSK DSMB monitors phase III trials and the DSMC monitors non-phase III trials. The DSMB/C have oversight over the following trials:

- MSK Investigator-Initiated Trials (IITs; MSK as sponsor)
- External studies where MSK is the data coordinating center
- Low risk studies identified as requiring DSMB/C review

The DSMC will initiate review following the enrollment of the first participant, or by the end of the year one if no accruals, and will continue for the study lifecycle until there are no participants under active therapy and the protocol has closed to accrual. The DSMB will initiate review once the protocol is open to accrual..

17.1 PROTECTION OF HUMAN SUBJECTS

Human Subjects Involvement, Characteristics, and Design

This study involves the treatment of human subjects with DS-3201b in combination with irinotecan on a phase I/II protocol.

The subject population will include patients, age 18 or over, with progressive or recurrent SCLC who have received at least one prior line of platinum-based chemotherapy. Patients must have a Karnofsky Performance Status $\geq 70\%$. Other inclusion and exclusion criteria will be specified in the protocol to ensure enrollment of patients with adequate hematologic and biochemical function, and no other serious medical conditions. Patients who are pregnant or lactating are excluded, and all patients must use appropriate methods of contraception. Up to 61 patients will be enrolled for both the Phase I and Phase II portions of the study across all sites.

Vulnerable populations will not be targeted for this research.

This study will be conducted at MSKCC and JHU. Participation of additional sites will require a protocol amendment.

Sources of Materials

The data collected from patients on the study will include demographics, medical history, medication records, toxicities, radiologic responses, and outcomes such as time to progression and survival.

Archived tissue samples as well as fresh biopsy samples will be collected for correlative studies to elucidate the mechanism of drug action.

The data collected for this study will be entered into a secure database (Medidata) at MSKCC. Source documentation will be available to support the computerized patient record.

The use and disclosure of protected health information will be limited to the individuals described in the Research Authorization form. A Research Authorization form must be completed by the Principal Investigator and approved by the IRB and Privacy Board (IRB/PB).

Potential Risks of DS-3201b

There are potential risks in the DS-3201b program that require monitoring. While these toxicities may be severe or life threatening, it is anticipated that they can be managed by clinical monitoring and intervention. Patients will be monitored for these potential toxicities and for unanticipated toxicities while they are receiving DS-3201b and for at least 30 days after their last dose of DS-3201b.

Potential Risks of DS-3201b Based on Current Ongoing Phase 1 Studies

- myelosuppression (thrombocytopenia, anemia, decreased lymphocyte count, decreased neutrophil count)
- dysgeusia
- alopecia
- diarrhea
- decreased appetite
- non-severe (Grade 1) QTc interval prolongation
- *Pneumocystis jirovecii* pneumonia

Potential Risks of DS-3201b Based on Findings from Animal Studies

- Dose-dependent QTc interval prolongation

It is possible that DS-3201b will have toxicities that were not observed in or predicted from the studies completed in rats and dogs, or have not yet been identified in patients, which may be severe or fatal.

For more detailed information, please consult the current Investigator's Brochure.

Subject participation is voluntary. The proposed study does not include patients under 18 years old. All patients will be required to sign a statement of informed consent that conforms to IRB guidelines. Informed consent will be documented by the use of a written consent form which has been approved by the IRB. Before protocol specified procedures are carried out, a study investigator or their staff explains the full details of the protocol and study procedures, as well as the risks involved to patients prior to their inclusion in the trial. Patients will also be informed that they are free to withdraw from the study at any time. The patient must be aware of the neoplastic nature of his/her disease and willingly consent after being informed of the procedures to be followed, the experimental nature of the therapy, alternatives, potential benefits, side effects, risks and discomforts. This consent is obtained in the clinic by one of the physician investigators whose name is indicated on the face page of the protocol. All patients must read, discuss with consenting physician, and sign an IRB approved consent form indicating their consent to participate. This consent form conforms to the applicable requirements of 21 CFR 50.25 elements of informed consent. Written consent will be obtained by either the principal investigator, co-principal investigators, or participating investigators. The original signed consent forms will become part of the patient's medical record. Each patient will receive a copy of the signed consent form. There is absolutely no waiver of the consent. Consent must be documented in the medical record of each patient.

Protections Against Risk: Procedures for protecting against and minimizing risks to treatment and other clinical interventions will be described within the text of the protocol. This includes toxicity monitoring, dose modification guidelines, and indications for removing patients from the study.

Potential Benefits of the Proposed Research to Human Subjects and Others

The potential benefits of the research to the patients are not known and there may be no benefit to the research subject. Administration of DS-3201b with irinotecan could potentially cause disease regression. The potential benefits of the research to others are not known but may include development of new therapies.

The risks to patients are reasonable in relation to the anticipated potential benefits for patients and others based on the preclinical and clinical data derived on the study drug to date.

Importance of the Knowledge to be Gained

The treatment of SCLC is an important unmet need that could impact thousands of potential patients. This approach would also provide a proof of concept for targeting the EZH2-SLFN11 pathway in patients with other tumor types that develop resistance to chemotherapy.

The risks to patients are reasonable in relation to the anticipated potential benefits for the patients and others, particularly given the broad potential of this therapy for SCLC and the impact on possible future therapies.

17.2 Privacy

MSK's Privacy Office may allow the use and disclosure of protected health information pursuant to a completed and signed Research Authorization form. The use and disclosure of protected health information will be limited to the individuals described in the Research Authorization form. A Research Authorization form must be completed by the Principal Investigator and approved by the IRB and Privacy Board (IRB/PB).

The consent indicates that individualized de identified information collected for the purposes of this study may be shared with other qualified researchers. Only researchers who have received approval from MSK will be allowed to access this information which will not include protected health information, such as the participant's name, except for dates. It is also stated in the Research Authorization that their research data may be shared with other qualified researchers.

17.3 Serious Adverse Event (SAE) Reporting

An adverse event is considered serious if it results in ANY of the following outcomes:

- Death
- A life-threatening adverse event
- An adverse event that results in inpatient hospitalization or prolongation of existing hospitalization
- A persistent or significant incapacity or substantial disruption of the ability to conduct normal life functions
- A congenital anomaly/birth defect
- Important Medical Events (IME) that may not result in death, be life threatening, or require hospitalization may be considered serious when, based upon medical judgment, they may jeopardize the patient or participant and may require medical or surgical intervention to prevent one of the outcomes listed in this definition
- Secondary malignancy as defined in section 11.2

Note: Hospital admission for a planned procedure/disease treatment is not considered an SAE.

SAE reporting is required as soon as the participant starts investigational treatment/intervention. SAE reporting is required for 30-days after the participant's last investigational treatment/intervention. Any event that occurs after the 30-day period that is unexpected and at least possibly related to protocol treatment must be reported.

Please note: Any SAE that occurs prior to the start of investigational treatment/intervention and is related to a screening test or procedure (i.e., a screening biopsy) must be reported.

All SAEs must be submitted in PIMS. If an SAE requires submission to the HRPP office per IRB SOP RR-408 'Reporting of Serious Adverse Events', the SAE report must be submitted within 5 calendar days of the event. All other SAEs must be submitted within 30 calendar days of the event.

The report should contain the following information:

- The date the adverse event occurred
- The adverse event
- The grade of the event
- Relationship of the adverse event to the treatment(s)
- If the AE was expected
- Detailed text that includes the following
 - An explanation of how the AE was handled
 - A description of the participant's condition
 - Indication if the participant remains on the study
- If an amendment will need to be made to the protocol and/or consent form
- If the SAE is an Unanticipated Problem

The SAE report should be completed as per above instructions. If appropriate, the report will be forwarded to the FDA by the IND Office

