Follow-up Period: Patients will be followed for survival every 3 months at routine clinic visits or via phone call if they are no longer being seen at MSKCC or JHU for a minimum of 2 years after the last dose of study drug treatment.

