An adverse event or suspected adverse reaction is considered "serious" if, in the view of either the investigator or sponsor, it results in any of the following outcomes: Death, a life-threatening adverse event, inpatient hospitalization or prolongation of existing hospitalization, a persistent or significant incapacity or substantial disruption of the ability to conduct normal life functions, or a congenital anomaly/birth defect. Important medical events that may not result in death, be life-threatening, or require hospitalization may be considered serious when, based upon appropriate medical judgment, they may jeopardize the patient or subject and may require medical or surgical intervention to prevent one of the outcomes listed in this definition.

Suspected adverse reaction means any adverse event for which there is a reasonable possibility that the drug caused the adverse event. For the purposes of IND safety reporting, "reasonable possibility" means there is evidence to suggest a causal relationship between the drug and the adverse event. Suspected adverse reaction implies a lesser degree of certainty about causality than adverse reaction, which means any adverse event caused by a drug.

Unexpected adverse event or unexpected suspected adverse reaction.

An adverse event or suspected adverse reaction is considered "unexpected" if it is not listed in the investigator brochure or is not listed at the specificity or severity that has been observed; or, if an investigator brochure is not required or available, is not consistent with the risk information described in the general investigational plan or elsewhere in the current application, as amended. "Unexpected," as used in this definition, also refers to adverse events or suspected adverse reactions that are mentioned in the investigator brochure as occurring with a class of drugs or as anticipated from the pharmacological properties of the drug, but are not specifically mentioned as occurring with the particular drug under investigation.

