11.3.2 Possible Treatment Emergent Adverse Events (TEAEs) for DS-3201b

COMMON:

- Platelet Count Decreased
- Altered taste (Dysgeusia)
- Anemia
- Neutrophil Count Decreased
- Alopecia
- White Blood Cell Count Decreased
- Lymphocyte Count Decreased
- Diarrhea
- Nausea

OCCASIONAL (Uncommon):

- Alanine Aminotransferase Increased
- Aspartate Aminotransferase Increased
- Decreased Appetite
- Common cold (Nasopharyngitis)
- Cough
- Fatigue
- Arthralgia
- Dyspnea
- Fever (Pyrexia)
- Pruritus
- Rash
- Dry Skin
- Gamma-Glutamyltransferase Increased

RARE:

- None

Contraindications regarding the use of DS-3201b in human subjects have not been established. DS-3201b is contraindicated for subjects with known hypersensitivity to either the drug substance or inactive ingredients in the drug product. No overdosages have been reported to date.

ADVERSE EVENTS OF SPECIAL INTEREST (AESI):

AESI include hepatic events that meet the potential Hy's Law criteria (defined as an elevated ALT and/or AST $\geq 3 \times$ ULN and an elevated TBL $> 2 \times$ ULN, regardless if it is due to disease progression per investigator assessment, which may occur at different time points during the study conduct), and secondary malignancy, including lymphoid malignancy.

Combined Elevations of Aminotransferases and Bilirubin

Hepatic events (both serious and non-serious) that meet the potential Hy's Law criteria defined as an elevated (ALT and/or AST) $\geq 3 \times$ ULN and an elevated TBL $> 2 \times$ ULN, regardless if it is due to disease progression per investigator assessment, that may occur at different time points during the study conduct, should always be reported to the sponsor. These events must be reported by eCRF, with the investigator's assessment of seriousness, severity, causality, and a detailed narrative. These events should be reported within 24 hours of investigator's awareness of the event regardless of seriousness.

If the subject discontinues study drug due to liver enzyme abnormalities, the subject should have additional clinical and laboratory evaluations in order to determine the nature and severity of the potential liver injury (including follow-up ALT, AST, TBL (including fractional), ALP and relevant hepatitis serology).

Secondary Malignancy

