A 3-month nonclinical toxicology study in rats administered DS-3201b showed the potential risks of developing lymphoid malignancies. A follow-up 3-month study in older rats performed to further understand the pathogenic mechanisms of this above finding in younger rats showed administration of DS-3201b to aged rats did not induce a lymphoma that had been previously observed with younger rats. In addition, no similar findings were noted in other 3-month animal toxicity studies of DS-3201b. In the ongoing clinical development program cases of secondary malignancies have been reported (see IB version 7 for additional details).

The treatment of subjects with an EZH2 inhibitor may increase the risk of developing a secondary T-cell malignancy. T-cell lymphomas have been observed in animals treated with DS-3201b and other agents that inhibit EZH2 in repeat-dose toxicology studies. A pediatric patient treated with an EZH2 inhibitor (tazemetostat) developed a secondary T-cell lymphoblastic lymphoma after approximately 15 months of therapy. A dose or duration of therapy at which agents that inhibit EZH2 would not increase the risk of a secondary T-cell malignancy is currently unknown.

Subjects receiving DS-3201b should further be monitored for signs and symptoms of toxicities suggestive of secondary malignancy. Any confirmed new diagnosis of secondary malignancy

should be reported as adverse events of special interest and reported to the sponsor in an expedited manner. Generally, these events should be reported as SAEs (with at least a seriousness criterion of important medical event, unless other criteria are met).

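### After day 30 the SAE rule in Section 17.3 is narrower than Section 11's duty to report any secondary malignancy, and no scheduled off-treatment contact asks about one

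*Combined protocol and SAP*

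**What the plan says.** Section 11, under the heading numbered 11.3.2, defines the adverse events of special interest as certain hepatic events "and secondary malignancy, including lymphoid malignancy". Its Secondary Malignancy text cites lymphoid tumours in rats, a pediatric case on another EZH2 inhibitor, and cases in this drug's own programme (referring to version 7 of the investigator brochure). It says that no dose or duration free of increased risk is known. "Any confirmed new diagnosis of secondary malignancy" is to be sent to the sponsor as an event of special interest on an expedited basis, and generally as an SAE.

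Section 17.3 names secondary malignancy among the SAE outcomes. It requires SAE reporting until 30 days after last treatment. Beyond that it says: "Any event that occurs after the 30-day period that is unexpected and at least possibly related to protocol treatment must be reported". Section 11 defines an event as unexpected "if it is not listed in the investigator brochure or is not listed at the specificity or severity that has been observed".

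On follow-up, Section 9.1 says: "Patients will be followed for survival every 3 months at routine clinic visits or via phone call", for at least 2 years after the last dose. Section 13.1 says that patients off study drug are followed for toxicity as well as survival. Section 17.1 promises toxicity monitoring for at least 30 days after the last dose.

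**The concern.** Two sections govern the same event, and one is narrower. Section 11 sends secondary malignancies down the SAE route, so a coordinator holding a late case will turn to Section 17.3, where the operational rule is. That rule carries two filters that Section 11 does not have, and it uses mandatory wording where Section 11 uses advisory wording.

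The second weakness is ascertainment. A duty to report works only for cases that come to light. If nobody is told to ask, a patient who has moved to another clinic and is reached by telephone about vital status may never mention a new diagnosis.

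At stake is the completeness of late safety information on a risk that the protocol itself singles out, in patients who also receive a DNA-damaging drug. Section 14.0 tabulates recorded toxicity, so a case that is never collected cannot appear in the tables.

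**Working it through.** The plan states no figure to reproduce on this point. The check sets the texts side by side and compares time windows.

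| Place | Window after last dose | Condition for reporting, or content |
|---|---|---|
| Section 11, Secondary Malignancy | None stated | Confirmed diagnosis only |
| Section 17.3, to day 30 | 30 days | Any SAE; secondary malignancy is listed |
| Section 17.3, after day 30 | Open | Unexpected **and** at least possibly related |
| Section 9.1, Follow-up Period | At least 2 years, 3-monthly | Survival |
| Section 13.1 | No interval or end stated | Toxicity and survival |
| Section 17.1 | At least 30 days | Toxicity monitoring |
| Section 10.1, Table 3.0 | Ends at the EOT visit | Adverse event monitoring |

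**Step 1: the two reporting rules.** Take a secondary malignancy confirmed after day 30. It is expected or unexpected, and possibly related or not: 2 × 2 = 4 combinations. Section 11 wants all 4 reported. The post-day-30 sentence in 17.3 requires 1 of the 4. The two rules differ for the other 3.

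**Step 2: can the filters close?**
- Expectedness turns on the investigator brochure. Section 11 says that the brochure gives details of cases in this drug's programme, so a site could class a late case as expected. The brochure is not among the documents, so this is a possibility only.
- Relatedness needs no brochure. Section 6.2 requires progression after a platinum doublet, so every patient brings an earlier treatment to which an investigator may attribute a new malignancy.

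**Step 3: would anyone ask?** Section 11's monitoring sentence is written for patients on drug: "Subjects receiving DS-3201b should further be monitored for signs and symptoms of toxicities suggestive of secondary malignancy". Section 13.1 places the EOT visit within 30 days of the last dose, and Table 3.0 has no later column. The only later contacts with a schedule are those in 9.1.
- Minimum follow-up: 2 × 365 = 730 days. Full SAE collection: 30 / 730 = 4.1%.
- Planned contacts: 24 months / 3 months = 8. Counting from the last dose, the first falls at about day 90, so none lies inside the 30-day window.

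**Step 4: deadlines.** Hepatic events of special interest have a 24-hour clock. Secondary malignancy has the word expedited and no number. Section 17.3 gives 5 calendar days where the institutional SAE policy applies, and otherwise: "All other SAEs must be submitted within 30 calendar days of the event".

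**The case against.** The strongest reply is that a known late case is already reportable. Section 11 sets no limits, and nothing in 17.3 says that its general rule overrides the special one. Read together, 17.3 adds a duty after day 30 and cancels none. This is a fair reading and probably the intended one. It does not answer the practical point: 17.3 does not restate the special duty, and no text says which rule governs.

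Several stronger readings are tempting, and the documents do not support them.

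- **Follow-up collects survival only.** Section 13.1 adds toxicity. What it lacks is an interval, an end date and a form.
- **The cited case shows a latency of about 15 months that outlasts the SAE window.** The text says that one pediatric patient on another EZH2 inhibitor "developed a secondary T-cell lymphoblastic lymphoma after approximately 15 months of therapy". That is time on drug and gives no interval after stopping. A patient treated that long would still be under full SAE reporting.
- **Late cases will be classed as expected.** The list of possible events for DS-3201b does not name secondary malignancy. The definition also keeps an event unexpected if it is anticipated only for the drug class, or is not listed at the observed specificity or severity. The outcome depends on a brochure not shown.
- **Expedited contradicts 30 days.** The 17.3 deadlines govern institutional submission. Exchange with the drug company is left to the Pharmacovigilance Agreement, and multicenter handling to an addendum. Neither is shown, and either may set a window or a deadline.
- **The cross-reference to section 11.2 in 17.3 is wrong.** Headings in Section 11 carry doubled numbers. The G-CSF heading reads 11.8 7 and is cited elsewhere as 11.7; by the same pattern 11.3.2 is 11.2. The reference is probably right and should be left alone.

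**Conclusion.** The point holds as a reconciliation of moderate scope and low severity. Applied literally, the post-day-30 rule in Section 17.3 can omit a named event of special interest that Section 11 wants reported, and nothing scheduled after the EOT visit asks about it.

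The size cannot be given as a number of lost cases, because the documents state no incidence. On the planned numbers the trial has 12 Phase I patients plus 25 further Phase II patients, 37 in all, so I assume that few cases would arise. No efficacy analysis is affected. A reader might infer that the trial fails to deliver an unbiased count of secondary malignancies, but no objective in Section 2.1 promises one.

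The conclusion assumes that the Pharmacovigilance Agreement and the multicenter addendum do not already set the window and instruct sites to ask. If they do, the remaining task is to make the protocol say the same.

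**What to change.** 1. In Section 17.3, state that secondary malignancy is reported under the Section 11 rule until the end of follow-up, whatever the 30-day limit, expectedness or relatedness.
2. Align Sections 9.1, 13.1 and 17.1 so that they describe one off-treatment follow-up, with content, interval and end date.
3. State one reporting deadline for secondary malignancy, consistent with the Pharmacovigilance Agreement.
4. Add one question to each 3-monthly contact: new malignancy yes or no, type, and date.

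The cost is protocol wording and one eCRF field at contacts already planned. The downside is a few more late reports, some of them unrelated to the drug; the investigator's causality assessment can be recorded with each.
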